12.4. Appendix 4: Collection of Pregnancy Information

- Investigator will collect pregnancy information on any female subject, who becomes pregnant while participating in this study
- Information will be recorded on the appropriate form and submitted to GSK within 2 weeks of learning of a subject's pregnancy.
- Subject will be followed to determine the outcome of the pregnancy. The investigator will collect follow up information on mother and infant, which will be forwarded to GSK. Generally, follow-up will not be required for longer than 6 to 8 weeks beyond the estimated delivery date.
- Any termination of pregnancy will be reported, regardless of fetal status (presence or absence of anomalies) or indication for procedure.
- While pregnancy itself is not considered to be an AE or SAE, any pregnancy complication or elective termination of a pregnancy will be reported as an AE or SAE.
- A spontaneous abortion is always considered to be an SAE and will be reported as such.
- Any SAE occurring as a result of a post-study pregnancy which is considered reasonably related
 to the study treatment by the investigator, will be reported to GSK as described in Section 12.6.
 Appendix 6. While the investigator is not obligated to actively seek this information in former
 study participants, he or she may learn of an SAE through spontaneous reporting.

Any female subject who becomes pregnant while participating

• will discontinue study medication or be withdrawn from the study

12.5. Appendix 5: Liver Safety Required Actions and Follow up Assessments Phase III-IV liver chemistry stopping and increased monitoring criteria have been designed to assure subject safety and evaluate liver event etiology (in alignment with the FDA premarketing clinical liver safety guidance).

Phase III-IV liver chemistry stopping criteria and required follow up assessments

Liver Chemistry Stopping Criteria - Liver Stopping Event				
ALT-absolute	ALT ≥ 8xULN			
ALT Increase	$ALT \ge 5xULN$ but $\le 8xULN$ persists for ≥ 2 weeks			
	ALT \geq 3xULN but $<$ 5xULN persists for \geq 4 weeks			
Bilirubin ^{1, 2}	ALT \geq 3xULN and bilirubin \geq 2xULN (>35% direct bilirubin)			
INR ²	ALT \geq 3xULN and INR>1.5, if INR measured			
Cannot	ALT \geq 5xULN but \leq 8xULN and cannot be monitored weekly for \geq 2 weeks			
Monitor	ALT \geq 3xULN but \leq 5xULN and cannot be monitored weekly for \geq 4 weeks			
Symptomatic ³	ALT ≥ 3 xULN associated with sy liver injury or hypersensitivity	imptoms (new or worsening) believed to be related to		
Required Action	ns and Follow up Assessments follow	wing ANY Liver Stopping Event		
Actions		Follow Up Assessments		
• Immediate	ly discontinue study treatment	Viral hepatitis serology ⁴		
• Report the	event to GSK within 24 hours	Only in those with underlying chronic		
• Complete	the liver event CRF and complete	hepatitis B at study entry (identified by		
an SAE da	ta collection tool if the event also	positive hepatitis B surface antigen) and		
meets the	criteria for an SAE ²	quantitative hepatitis B DNA		
• Perform liver event follow up assessments		Blood sample for pharmacokinetic (PK)		
 Monitor the subject until liver chemistries 		analysis, obtained within 24 hours after las		
	abilize, or return to within baseline	dose ⁵		
	ITORING below)	• Serum creatine phosphokinase (CPK) and		
• Do not res	start/rechallenge subject with	lactate dehydrogenase (LDH).		
	ment unless allowed per protocol	• Fractionate bilirubin, if total		
=	Medical Governance approval is	bilirubin≥2xULN		
granted		Obtain complete blood count with		
• If restart/rechallenge not allowed or not		differential to assess eosinophilia		
granted , permanently discontinue study		Record the appearance or worsening of		
treatment and may continue subject in the		clinical symptoms of liver injury, or		
study for any protocol specified follow up		hypersensitivity, on the AE report form		
assessments		Record use of concomitant medications on		
•		the concomitant medications report form		
MONITORING:		including acetaminophen, herbal remedies.		
	r INR criteria:	other		
• Repeat liver chemistries (include ALT, AST,		• over the counter medications.		
alkaline phosphatase, bilirubin) and perform		Record alcohol use on the liver event		

liver event follow up assessments within 24 hrs

- Monitor subjects twice weekly until liver chemistries resolve, stabilize or return to within baseline
- A specialist or hepatology consultation is recommended

For All other criteria:

- Repeat liver chemistries (include ALT, AST, alkaline phosphatase, bilirubin) and perform liver event follow up assessments within
 24-72 hrs
- Monitor subjects weekly until liver chemistries resolve, stabilize or return to within baseline

alcohol intake case report form

For bilirubin or INR criteria:

- Anti-nuclear antibody, anti-smooth muscle antibody, Type 1 anti-liver kidney microsomal antibodies, and quantitative total immunoglobulin G (IgG or gamma globulins).
- Serum acetaminophen adduct HPLC assay (quantifies potential acetaminophen contribution to liver injury in subjects with definite or likely acetaminophen use in the preceding week [James, 2009]).
- Liver imaging (ultrasound, magnetic resonance, or computerised tomography) and /or liver biopsy to evaluate liver disease; complete Liver Imaging and/or Liver Biopsy CRF forms.
- 1. Serum bilirubin fractionation should be performed if testing is available. If serum bilirubin fractionation is not immediately available, discontinue study treatment for that subject if $ALT \ge 3xULN$ and bilirubin $\ge 2xULN$.
- 2. All events of ALT ≥ 3xULN and bilirubin ≥ 2xULN (>35% direct bilirubin) or ALT ≥ 3xULN and INR>1.5, if INR measured which may indicate severe liver injury (possible 'Hy's Law'), must be reported as an SAE (excluding studies of hepatic impairment or cirrhosis); INR measurement is not required and the threshold value stated will not apply to subjects receiving anticoagulants
- 3. New or worsening symptoms believed to be related to liver injury (such as fatigue, nausea, vomiting, right upper quadrant pain or tenderness, or jaundice) or believed to be related to hypersensitivity (such as fever, rash or eosinophilia)
- 4. Includes: Hepatitis A IgM antibody; Hepatitis B surface antigen and Hepatitis B Core Antibody (IgM); Hepatitis C RNA; Cytomegalovirus IgM antibody; Epstein-Barr viral capsid antigen IgM antibody (or if unavailable, obtain heterophile antibody or monospot testing); Hepatitis E IgM antibody or Hepatitis E RNA
- 5. PK sample may not be required for subjects known to be receiving placebo or non-GSK comparator treatments. Record the date/time of the PK blood sample draw and the date/time of the last dose of study treatment prior to blood sample draw on the CRF. If the date or time of the last dose is unclear, provide the subject's best approximation. If the date/time of the last dose cannot be approximated OR a PK sample cannot be collected in the time period indicated above, do not obtain a PK sample. Instructions for sample handling and shipping are in the SRM.

Phase III-IV liver chemistry increased monitoring criteria with continued therapy

Liver Chemistry Increased Monitoring Criteria – Liver Monitoring Event			
Criteria	Actions		
	Notify the GSK medical monitor within 24 hours		
ALT ≥5xULN and <8xULN and bilirubin	of learning of the abnormality to discuss subject		
<2xULN without symptoms believed to be related to liver injury or	safety.		
hypersensitivity, and who can be	Subject can continue study treatment		
monitored weekly for 2 weeks.	Subject must return weekly for repeat liver		
OR			

ALT ≥ 3 xULN and < 5xULN and bilirubin < 2xULN without symptoms believed to be related to liver injury or hypersensitivity, and who can be monitored weekly for 4 weeks.

- chemistries (ALT, AST, alkaline phosphatase, bilirubin) until they resolve, stabilise or return to within baseline
- If at any time subject meets the liver chemistry stopping criteria, proceed as described above
- If ALT decreases from ALT ≥5xULN and <8xULN to ≥3xULN but <5xULN, continue to monitor liver chemistries weekly.
- If, after 4 weeks of monitoring, ALT <3xULN and bilirubin <2xULN, monitor subjects twice monthly until liver chemistries normalize or return to within baseline.

References

12.6.1. Definition of Adverse Events

Adverse Event Definition:

- An AE is any untoward medical occurrence in a patient or clinical investigation subject, temporally associated with the use of a medicinal product, whether or not considered related to the medicinal product.
- NOTE: An AE can therefore be any unfavorable and unintended sign (including an abnormal laboratory finding), symptom, or disease (new or exacerbated) temporally associated with the use of a medicinal product.

Events meeting AE definition include:

- Any abnormal laboratory test results (hematology, clinical chemistry, or urinalysis) or other safety assessments (e.g., ECGs, radiological scans, vital signs measurements), including those that worsen from baseline, and felt to be clinically significant in the medical and scientific judgement of the investigator.
- Exacerbation of a chronic or intermittent pre-existing condition including either an increase in frequency and/or intensity of the condition.
- New conditions detected or diagnosed after study treatment administration even though it may have been present prior to the start of the study.
- Signs, symptoms, or the clinical sequelae of a suspected interaction.
- Signs, symptoms, or the clinical sequelae of a suspected overdose of either study treatment or a
 concomitant medication (overdose per se will not be reported as an AE/SAE unless this is an
 intentional overdose taken with possible suicidal/self-harming intent. This should be reported
 regardless of sequelae).
- "Lack of efficacy" or "failure of expected pharmacological action" per se will not be reported as an AE or SAE. However, the signs and symptoms and/or clinical sequelae resulting from lack of efficacy will be reported if they fulfil the definition of an AE or SAE.

Events **NOT** meeting definition of an AE include:

- Any clinically significant abnormal laboratory findings or other abnormal safety assessments
 which are associated with the underlying disease, unless judged by the investigator to be more
 severe than expected for the subject's condition.
- The disease/disorder being studied or expected progression, signs, or symptoms of the disease/disorder being studied, unless more severe than expected for the subject's condition.
- Medical or surgical procedure (e.g., endoscopy, appendectomy): the condition that leads to the procedure is an AE.
- Situations where an untoward medical occurrence did not occur (social and/or convenience admission to a hospital).
- Anticipated day-to-day fluctuations of pre-existing disease(s) or condition(s) present or detected at the start of the study that do not worsen.

12.6.2. Definition of Serious Adverse Events

If an event is not an AE per definition above, then it cannot be an SAE even if serious conditions are met (e.g., hospitalization for signs/symptoms of the disease under study, death due to progression of disease, etc).

Serious Adverse Event (SAE) is defined as any untoward medical occurrence that, at any dose:

a. Results in death

b. Is life-threatening

NOTE:

The term 'life-threatening' in the definition of 'serious' refers to an event in which the subject was at risk of death at the time of the event. It does not refer to an event, which hypothetically might have caused death, if it were more severe.

c. Requires hospitalization or prolongation of existing hospitalization

NOTE:

- In general, hospitalization signifies that the subject has been detained (usually involving at least an overnight stay) at the hospital or emergency ward for observation and/or treatment that would not have been appropriate in the physician's office or out-patient setting. Complications that occur during hospitalization are AEs. If a complication prolongs hospitalization or fulfills any other serious criteria, the event is serious. When in doubt as to whether "hospitalization" occurred or was necessary, the AE should be considered serious.
- Hospitalization for elective treatment of a pre-existing condition that did not worsen from baseline is not considered an AE.

d. Results in disability/incapacity

NOTE:

- The term disability means a substantial disruption of a person's ability to conduct normal life functions.
- This definition is not intended to include experiences of relatively minor medical significance such as uncomplicated headache, nausea, vomiting, diarrhea, influenza, and accidental trauma (e.g. sprained ankle) which may interfere or prevent everyday life functions but do not constitute a substantial disruption

e. Is a congenital anomaly/birth defect

f. Other situations:

- Medical or scientific judgment should be exercised in deciding whether reporting is appropriate
 in other situations, such as important medical events that may not be immediately life-threatening
 or result in death or hospitalization but may jeopardize the subject or may require medical or
 surgical intervention to prevent one of the other outcomes listed in the above definition. These
 should also be considered serious.
- Examples of such events are invasive or malignant cancers, intensive treatment in an emergency room or at home for allergic bronchospasm, blood dyscrasias or convulsions that do not result in hospitalization, or development of drug dependency or drug abuse

g. Is associated with liver injury and impaired liver function defined as:

- ALT \geq 3xULN and total bilirubin* \geq 2xULN (>35% direct), or
- ALT ≥ 3 xULN and INR** > 1.5.

- * Serum bilirubin fractionation should be performed if testing is available; (for ND patients only) if unavailable, record presence of detectable urinary bilirubin on dipstick, indicating direct bilirubin elevations and suggesting liver injury. If fractionation is unavailable and ALT \geq 3xULN and total bilirubin \geq 2xULN, then the event is still to be reported as an SAE.
- ** INR testing not required per protocol and the threshold value does not apply to subjects receiving anticoagulants. If INR measurement is obtained, the value is to be recorded on the SAE form.

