7.4.1.4. Cardiovascular and Death Events

For any cardiovascular events detailed in Section 12.6. Appendix 6 and all deaths, whether or not they are considered SAEs, specific Cardiovascular (CV) and Death sections of the CRF will be required to be completed. These sections include questions regarding cardiovascular (including sudden cardiac death) and non-cardiovascular death.

The CV CRFs are presented as queries in response to reporting of certain CV Medical Dictionary for Regulatory Activities (MedDRA) terms. The CV information should be recorded in the specific cardiovascular section of the CRF within one week of receipt of a CV Event data query prompting its completion.

The Death CRF is provided immediately after the occurrence or outcome of death is reported. Initial and follow-up reports regarding death must be completed within one week of when the death is reported.

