7.4.2. Adverse Events of Special Interest

The investigator (or subinvestigator) or designee will be responsible for detecting, documenting, and reporting any AEs of special interest listed below. These events have been identified based on the known safety profiles of ESAs, theoretical or potential risks based on the mechanism of action of daprodustat, and findings from completed nonclinical studies of daprodustat.

- Thrombosis and/or tissue ischemia secondary to excessive erythropoiesis
- Death, myocardial infarction, stroke, heart failure, thromboembolic events, thrombosis of vascular access
- Cardiomyopathy
- Pulmonary artery hypertension (PAH)
- Cancer-related mortality and tumor progression and recurrence
- Esophageal and gastric erosions
- Proliferative retinopathy, macular edema, choroidal neovascularization
- Exacerbation of rheumatoid arthritis

Any relevant AE should be recorded in the relevant section of the subject's eCRF.

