## 8.2. Adverse Events of Special Interest Analyses

A comprehensive list based on clinical review will be used to identify each type of event. AEs of special interest will be manually-selected before unblinding at patient-level (i.e. following case-by-case review by members of the Safety Review Team (SRT) including representatives from the local Japan team) and not at preferred term level. The details of the planned displays are provided in [Appendix 10: List of Data Displays](#).

Endpoint / Parameter/ Display Type	Absolute		
	Summary		Individual
	T	F	L
AEs of special interest 			
On-Therapy AEs of special interest	Y		Y
Post-therapy AEs of special interest	Y		Y

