**CONFIDENTIAL**

201754

ICH Listings					
No.	Population	IDSL / TST ID / Example Shell	Title	Programming Notes	SAC
Serious and Other Significant Adverse Events					
25.	Safety	AE8	Listing of Fatal Serious Adverse Events	ICH E3	Y
26.	Safety	AE8	Listing of Non-Fatal Serious Adverse Events	ICH E3	Y
27.	All Screening	AE8	Listing of Serious AEs in Screening Period		Y
28.	Safety	AE8	Listing of Adverse Events Leading to Withdrawal from Study / Permanent Discontinuation of Study Treatment	ICH E3	Y
29.	Safety	AE14	Listing of Reasons for Considering as a Serious Adverse Event	ICH E3	Y
30.	Safety	SAFE_L1	Listing of Adverse Events of Special Interest	ICH E3 Displays will be produced with AESI category in addition of AE8 template.	Y
All Laboratory					
31.	Safety	LB5	Listing of All Chemistry Data for Subjects with Any Value Outside of Normal Range/of PCI	ICH E3	Y
32.	Safety	LB5	Listing of All Hematology Data for Subjects with Any Value Outside of Normal Range/of PCI	ICH E3	Y
33.	Safety	LB5	Listing of All Other Laboratory Data for Subjects with Any Value Outside of Normal Range/of PCI	ICH E3	Y

CONFIDENTIAL

201754

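### Protocol 12.6.2, combined with AE-based SAP tables, may leave deaths or anemia admissions judged to be expected disease course out of the by-arm SAE and AESI counts

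*Protocol*

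**What the plan says.** Protocol 12.6.2 opens with a gate: what is not an AE cannot be an SAE, "even if serious conditions are met (e.g., hospitalization for signs/symptoms of the disease under study, death due to progression of disease". The same section then lists a fatal outcome and hospitalization among the SAE criteria.

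Protocol 12.6.1 sets the AE definition that the gate relies on. It leaves out the disease under study and its expected course, except where the investigator finds it worse than anticipated for that subject. It also counts exacerbation of a pre-existing condition as an AE. On lack of efficacy it says that "clinical sequelae resulting from lack of efficacy will be reported if they fulfil the definition of an AE or SAE".

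Protocol 7.4.2, repeated in SAP 15.6.4, lists this AESI category with no exception for disease progression: "Death, myocardial infarction, stroke, heart failure, thromboembolic events, thrombosis of vascular access".

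Protocol 7.4.1.4 requires the CV and Death sections of the CRF for "all deaths, whether or not they are considered SAEs", to be completed within one week of the report. Protocol 7.4.1.1 requires SAEs to reach the sponsor within 24 hours.

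SAP 8.1.1 counts subjects with at least one serious AE. SAP 8.2 says that "AEs of special interest will be manually-selected before unblinding at patient-level". In SAP Appendix 10, Listing 25 is the "Listing of Fatal Serious Adverse Events", and Listing 81 is a patient profile listing of deaths.

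**The concern.** Protocol Appendix 2 records that marketed ESAs are associated with an increased risk of death and serious cardiovascular events. Its mitigation is in-stream monitoring of AESIs by the internal safety review team. The comparison of daprodustat with an ESA on death should therefore rest on a count that does not depend on the cause the investigator assigns. The gate in 12.6.2 makes it depend on that judgment.

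The hospitalization example raises a second problem. An admission for symptomatic anemia is the direct clinical consequence of failed Hgb control. The lack-of-efficacy sentence in 12.6.1 points towards recording it, while the example in 12.6.2 points away. Two sites could handle the same admission differently, and both could cite the protocol.

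**Working it through.** The documents state no figure to reproduce, so the check follows one event through the definitions and outputs.

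1. **AE status.** A subject dies, and the investigator attributes the death to the expected course of the disease. Under 12.6.1 this is not an AE unless it is judged worse than anticipated.
2. **SAE status.** If it is not an AE, 12.6.2 removes it from the SAEs although its outcome is fatal. Death is one of the two examples given there.
3. **SAE outputs.** Tables 3.17, 3.18 and 3.20 and Listing 25 are defined on serious AEs, so the death is not in them.
4. **AESI outputs.** SAP 8.2 and 15.6.4 select AESIs from AEs by case review. Neither says that deaths known only from the Death CRF enter that review. Tables 3.22 and 3.23 may therefore omit the death. The category also pools death with MI, stroke, heart failure and thrombosis, and SAP 8.2.1 summarizes by AESI term, so even a counted death may not be shown separately.
5. **What remains.** The Death CRF is completed. Listing 81 shows the death but gives no count by arm. Table 1.1 tabulates subject status and withdrawal reasons by arm and might show deaths, but it is not defined on them. The headline deliverable (SAP 15.10.3) contains Tables 1.1, 3.17 and 3.22 and omits Listing 81.
6. **Timing.** A death outside the SAE route falls under the one-week deadline of 7.4.1.4 instead of the 24 hours of 7.4.1.1.
7. **Anemia admissions.** The same path applies, but with no separate CRF as a safety net. The by-arm summaries of Hgb below 7.5 g/dL (SAP 7.3.2) and of blood products (SAP 6.2) capture severe anemia but do not count admissions.

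**Effect on a comparison.** Let p1 and p2 be the true death proportions, and let the same fraction q of deaths be left out in each arm. The observed difference is (1 − q)(p1 − p2), which shrinks. The observed ratio is (1 − q)p1 / [(1 − q)p2] = p1/p2, which is unchanged.

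**Size.** The documents give no expected number of deaths and no attribution rate. As an illustration on assumed values only, take one-year mortality of 3% to 8% in 135 subjects per arm: 135 × 0.03 = 4.05 and 135 × 0.08 = 10.8 deaths. If 5% to 30% of these were attributed to disease progression, 4.05 × 0.05 = 0.2 to 10.8 × 0.30 = 3.2 deaths per arm would leave the counts. If no investigator uses the rule, the number is zero.

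**The case against.** A reader might infer that 12.6.2 bars every disease-related death or admission from being an SAE. The documents do not support that. The gate works only through 12.6.1, under which disease worse than expected, exacerbations, and qualifying sequelae of lack of efficacy are all AEs. Subjects enter on a single ESA used for at least 10 weeks, with Hgb of 9.5 to 12.5 g/dL, so an admission for symptomatic anemia would often qualify as an exacerbation.

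The death route is also narrow if the disease is the anemia itself. Protocol 6.10 does not regard the target disease as a threat to life, so a fatal course would ordinarily exceed expectation and become an SAE. Fatal MI, stroke and heart failure are named separately as AESIs. Deaths are not lost to the study, since the Death CRF and Listing 81 hold them. The AESI list names death outright, and no section says that a disease-attributed death is dropped from it.

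All of this stands, and it limits the point to events that may be missed. It does not close the gap. Whether an event exceeds expectation remains the investigator's judgment. The death example in 12.6.2 steers that judgment the wrong way. No section says whether progression means anemia or CKD, or that Death CRF records feed any by-arm table.

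A reader might also infer a bias towards no difference between arms. With equal attribution under double-blinding, that holds for the absolute difference but not for the ratio. The safety analyses are descriptive, so no formal test of deaths is affected.

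**Conclusion.** The point holds as a conflict between definitions plus a missing derivation. The plan allows a death or an anemia admission judged to be expected disease course to be absent from the by-arm SAE and AESI counts, and allows such a death to take the slower reporting route. It does not show that any death will be missed.

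The number cannot be derived from the documents. It is probably small if the disease is anemia, larger if sites read it as CKD, and may be nil. The illustrative 0.2 to 3.2 deaths per arm rests wholly on assumed rates and carries no weight in this conclusion. The change is worth making because death is a named risk of the comparator class, the data are already collected, and the remedy costs almost nothing.

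**What to change.** 1. In SAP 15.6.4, take the death component of the AESI from the Death CRF, covering all deaths on-therapy and post-therapy. Add to Appendix 10 a count of all deaths by treatment group.
2. In Protocol 12.6.2, remove the two examples. Make the matching edit to the disease exclusion in 12.6.1, because changing 12.6.2 alone would leave the two sections in conflict. State that every death is recorded as an SAE, with the attributed cause in the causality field. This brings both sections into line with 7.4.1.4 and 7.4.2.
3. Define the disease under study, saying whether it means the anemia or the underlying CKD. Reconcile the hospitalization example with the lack-of-efficacy sentence in 12.6.1, so that admissions for worsened anemia are recorded in the same way at every site.

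A rule making every unplanned hospitalization an SAE would go beyond the defect and is not needed. The cost is a few sentences in Protocol Appendix 6, one derivation line and one table in the SAP, and a few extra SAE forms. No new death data have to be collected.
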